### i. Times

1. Initial Epidural Bolus (Labor Epidural Initiation)
2. Time of each anesthesia intervention request
3. Pain scores
4. Delivery

### ii. Cervical Exam (Dilatation (cm); performed by RN or Obstetrician)

1. Epidural Placement (if known; c/in 2 hrs before/after)
2. At time of request for additional analgesia (if known)

### iii. Verbal Pain Scores (0-10; average pain at peak of contractions; obtained by investigator):

1. Initial epidural request
2. 30 mins s/p epidural initial dosing (average peak of last contraction)
3. q 1 hour (average pain at peak of contractions)
4. At request for addl analgesia
  - a. 30 mins s/p top-up
5. At time of exam that establishes complete cervical dilatation (if known)
6. Average peak pain score during pushing (obtained c/in 1 hour post-partum)

### iv. Additional Data Points

1. Overall Satisfaction c Labor Analgesia (0-100%; measured c/in 1 hr of delivery)
2. Labor Outcome: Spontaneous/Instrumented/Cesarean and total number of hours of oxytocin infusion prior to delivery
3. Neonatal Apgars (1 and 5 mins; assigned by pediatrician)
4. Pruritus q2 hrs (Y/N)
  - a. Requiring treatment
5. Nausea (0-10) Vomiting q2 hrs Y/N
  - a. Requiring treatment
6. Hypotension Requiring Treatment (Y/N)
7. Motor Weakness c Labor Analgesia (q2 hours; Straight leg raise Y/N)
8. Sensory level q2hrs
9. Duration of first and second stage of labor
10. Rupture of membranes (spontaneous or artificial) prior to epidural

*Inclusion criteria:* ASA I & II, Nulliparous and Multiparous, Spontaneous/Induced/Augmented Labor, Early active labor (cervix <5 cm (if known)), Pain (VPS) > 3, 18-45 years of age.

*Exclusion criteria:* <37 weeks gestation, H/o Cesarean Section, Multiple Gestation, Pre-eclampsia, Narcotics within 3 hours prior to labor epidural placement, Chronic Pain (as defined by chronic opiate consumption), Women who are participating in another study that will impact protocol

Our primary outcome or determinant of different treatments for labor pain is the minimal local anesthetic concentration of the final participants in each respective group upon study completion.

Interim analysis will be performed at 20 patients (10 in each group) in study part A and B, respectively. If

no important differences are detected, the study will end with the recruitment of 160 patients (80 for each study group) per our sample size calculation, based off an MLAC study by Ginosar, et al.

Demographic, obstetric and clinical outcome measures data will be analyzed using unpaired Student's, Mann-Whitney U-test, and Chi-Squared or Fisher's exact test as appropriate.

MLAC analysis: The median effective concentrations will be estimated from the up-down sequences using the method of Dixon and Massey (Dixon WJ, Massey FJ. Introduction to statistical analysis. 4th ed. New York: McGraw-Hill, 1983) that will enable MLAC with 95% confidence interval (CI) to be derived. The sequences will also be subjected to Wilcoxon and Litchfield probit regression analyses using  $\ln(1+x)$  transform as back-up or sensitivity tests.

*DATA SAFETY MONITORING PLAN* will follow standard of clinical care. Any adverse events will be reported to the PI and necessary adjustments to the protocol will be immediately instituted.

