**General background**

Ginosar, et al. performed a minimal local anesthetic (MLAC) study comparing intravenous fentanyl with epidural fentanyl (continuous infusion) in the setting of a continuous epidural infusion of bupivacaine for labor analgesia. These findings were suggestive of a predominately spinal mechanism of action of epidural opioids.

A recent meta-analysis by George, et al. found a local anesthetic sparing effect and improved maternal satisfaction in the setting of labor epidural analgesia with programmed intermittent boluses (PIEB) of local anesthetic and short acting opioids compared with continuous epidural infusions (CEI). This finding in favor of automated intermittent boluses of solution for the maintenance of labor analgesia has popularized the technique. It remains unclear if the advantageous effects of PIEB are from the potentially greater spread of solution associated with the bolus or the bolus administration of opioids into the epidural space enhancing a potential concentration effect across with the intrathecal space. Given that the mechanism of action of epidural opioids remains poorly characterized, the effect of bolusing epidural opioids may alter the pharmacodynamic profile.

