**Experimental design**

Pregnant women who present to Labor and Delivery for an anticipated vaginal delivery will be identified as potential participants based on inclusion/exclusion criteria and their desire for labor epidural analgesia. Once identified, interested candidates will be fully informed of the study procedures, have all

questions answered, and informed consent obtained. Pregnant participants will receive a labor epidural upon the patient's request and the epidural catheter will be initiated with 15 ml 0.125% bupivacaine with 10 mcg of sufentanil (our current standard of care loading dose).

Patients will be randomized into 1 of 4 group. Either group I or II in Study Part A and group III or IV in Study Part B in a double-blinded design. Each study part will run in parallel and independently. We have separated the study into 2 parts to clarify the methodology and aims for purposes of IRB and study design protocols.

*Study Part A:*

Group 1 Starting Concentration CEI: Bupivacaine 0.06% at 10 ml/hour + Sufentanil 5 mcg (2 ml) /hour (start at 0 mins)

Group 2 Starting Concentration PIEB: Bupivacaine 0.06% 10 ml q 60 + Sufentanil 5 mcg (2 ml) q60 (start at 30 mins)

Top-Up: 5-15ml 0.25% bupivacaine for all instances of request of additional analgesia (a current standard of care treatment option for breakthrough pain)

Bupivacaine 0.06% mg/ml in 250 ml NS bag and sufentanil 2.5 mcg/ml in 100 ml NS bag.

\*Top-up is an additional dose provided upon patient request in the setting of inadequate analgesia during labor. Bupivacaine concentration to increase or decrease by 0.01% in subsequent patient depending on success or failure of previous patient

*Study Part B:*

Group 3: CEI Bupivacaine 0.06% 10 ml/hour + PIEB Sufentanil 5 mcg (2 ml) bolus q60 mins

Group 4: PIEB: Bupivacaine 0.06% 10 ml q 60 mins + CEI Sufentanil 5 mcg (2 ml)/hr continuous infusion 0.5 mcg/ml

PIEB start at 30 mins and CEI start at 0 mins.

Top-Up: 5-15ml 0.25% bupivacaine for all instances of request of additional analgesia (a current standard of care treatment option for breakthrough pain)

Bupivacaine 0.06% mg/ml in NS; 250 ml bag.

Sufentanil bag 2.5 mcg/ml in NS; 100 ml bag.

Bupivacaine concentration to increase or decrease by 0.01% in subsequent patient depending on success or failure of previous patient. Protocol success/failure/reject in each group (which will affect the subsequent patient's dose in the randomized group) will be determined by the following criteria:

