Success - No supplemental analgesia request until vaginal exam c/w 8 cm dilation or more -> 0.01% w/v reduction in subsequent participant's local anesthetic.

Failure - Supplemental analgesia request c vaginal exam c/w less than 8 cm dilatation ->0.01% w/v increase in subsequent LA infusion.

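### The up-down rule holds each group near a 50% request rate, so the unadjusted secondary tests cannot show a mode effect that acts through analgesic adequacy, and the plan neither adjusts for concentration nor says so

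*Combined protocol and SAP*

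**What the plan says.** The dosing rule is in Experimental design: "Bupivacaine concentration to increase or decrease by 0.01% in subsequent patient depending on success or failure of previous patient". The two outcomes that drive it are "Success - No supplemental analgesia request until vaginal exam c/w 8 cm dilation or more", which lowers the next woman's concentration in that group, and "Failure - Supplemental analgesia request c vaginal exam c/w less than 8 cm dilatation", which raises it. A rejected woman leaves the concentration unchanged and receives no study number. The Part A groups share a starting point ("Group 1 Starting Concentration CEI: Bupivacaine 0.06% at 10 ml/hour"; "Group 2 Starting Concentration PIEB: Bupivacaine 0.06% 10 ml q 60"), and both Part B groups are also given as 0.06%. Every request for more analgesia is answered with a top-up.

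Under iv. Additional Data Points, the primary outcome is the MLAC, estimated by the Dixon and Massey method with a 95% confidence interval and backed up by probit regression. For everything else the plan is one sentence: "Demographic, obstetric and clinical outcome measures data will be analyzed using unpaired Student's, Mann-Whitney U-test, and Chi-Squared or Fisher's exact test as appropriate". The measures it covers include repeated pain scores, satisfaction, motor weakness and hypotension. Request times are also collected, but no test of the request proportion is named. Nothing says that these comparisons will take account of the concentration received, or that concentrations are titrated to response.

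General background cites a meta-analysis whose result, relative to continuous infusion, is described as "local anesthetic sparing effect and improved maternal satisfaction in the setting of labor epidural analgesia with programmed intermittent boluses (PIEB".

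**The concern.** A one-up/one-down rule steers each group towards the concentration at which half the women request more analgesia, whatever the delivery mode. If PIEB is the more potent mode, its group drifts to a weaker solution until its request rate matches that of CEI. Two-sample tests that ignore concentration then compare groups which the design has made about equally effective.

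Two misreadings follow. A null on pain, requests or satisfaction could be taken as evidence that the modes are equivalent, and could seem to contradict a real MLAC difference; the background mentions satisfaction as a PIEB benefit, so the temptation is there. In the other direction, a difference in motor weakness or hypotension could be credited to mode when it partly or wholly reflects a different bupivacaine concentration.

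**Working it through.** **Inputs from the plan.** Start 0.06%, step 0.01%, success lowers and failure raises (Experimental design). Sample size: "the study will end with the recruitment of 160 patients (80 for each study group". With four groups this can mean 40 or 80 women per group, so both are used. The plan gives no alpha, power, effect size or SD, so its sample size cannot be reproduced. Two-sided 0.05 is assumed below.

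**Step 1: an identity that needs no model of response.** Let n be the evaluable women in a group and k the number of steps from 0.06% to the concentration reached after the last of them. Each failure adds one step and each success removes one, so

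- failures − successes = k, and failures + successes = n;
- request proportion = 1/2 + k/(2n);
- difference between two groups = (k₁ − k₂)/(2n).

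A final gap of 0.03% is 3 steps: 3/80 = 3.75 percentage points with n = 40, and 3/160 = 1.9 points with n = 80.

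**Step 2: the gap needed for significance.** Near 50%, the smallest significant difference is 1.96 × √(2 × 0.25/n).

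| n per group | Difference needed | Steps (2n × difference) | Concentration gap |
|---|---|---|---|
| 40 | 0.219 | 17.5 | 0.175% |
| 80 | 0.155 | 24.8 | 0.25% |

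Both gaps are far larger than the 0.06% starting concentration.

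**Step 3: simulation of the rule.** Assumptions: normal tolerance distribution, SD 0.01% to 0.03%, true EC50s between 0.03% and 0.10%, concentration floored at 0%, 10,000 runs per scenario, pooled z test.

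- With EC50 0.08% (CEI) and 0.04% (PIEB) and SD 0.02%, request rates were 52.5% v 47.5% (n = 40) and 51.3% v 48.7% (n = 80). The identity predicts a 4-step gap: 4/80 = 5.0 and 4/160 = 2.5 points.
- At a fixed 0.06% the same EC50s would give 84% v 16%, since 0.06% lies one SD below the first and one SD above the second.
- The test of requests rejected in 0.0% of runs in every scenario, below even the nominal 5%. A fixed 0.06% in both groups would detect an EC50 gap of 0.02% with power of 67% to about 100% (n = 40) or 92% to about 100% (n = 80).
- Exception: if the PIEB EC50 is at or below zero, the floor stops the titration. With n = 40 and the CEI EC50 at 0.06%, the PIEB request rate was 33% at EC50 0 and 23% at −0.01%, and the test rejected in 18% and 88% of runs.

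**Step 4: other outcomes, same simulation.** Each response model is assumed.

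| Outcome model | Unadjusted rejection, n = 40 | n = 80 |
|---|---|---|
| Pain depends only on request status (2-point shift, SD 2) | 2.6–4.0% | 2.5–3.7% |
| Same, plus a direct 1-point mode effect | 50–64% | 83–88% |
| Motor weakness rises with concentration, EC50 gap 0.02–0.06% | 29–100% | 49–100% |

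**Step 5: what adjustment recovers.** This uses EC50s of 0.08% or 0.07% v 0.05% and SD 0.01% to 0.02%. If pain is linear in the shortfall of concentration below tolerance, the unadjusted t test rejected in 2–5% of runs, and a regression on group plus concentration in 87–100%. If pain depends only on request status, the adjusted test rejected in 26–55% (n = 40) or 33–82% (n = 80). The share of women in the concentration range common to both groups (CEI 5th to PIEB 95th percentile) ran from 11% to 61%. It was lowest, at 11–13%, for 0.08% v 0.05% with SD 0.01%.

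**The case against.** The plan assigns relative potency to the MLAC, in Specific aims, in the primary outcome and again in Significance. A PIEB advantage would appear there as a lower MLAC. Success and failure are analysed by Dixon and Massey and by probit, which is the right use of that endpoint, and no test of the request proportion is named. Satisfaction enters the background as another study's finding and is not stated as an aim. Comparing secondary outcomes at equi-effective concentrations is also a legitimate question, arguably the useful one for motor weakness and hypotension. All of this stands, and it limits the point to how the secondary comparisons are analysed and read.

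A reader might infer that the trial cannot show a PIEB advantage, or that every secondary test is null by construction. The documents support neither. The MLAC contrast is intact. Pain and satisfaction are not the titrated endpoint: scores are also taken after top-ups, at full dilatation and for the pushing stage, and a direct mode effect could be detected there, as Step 4 shows. Outcomes that follow concentration are not null at all.

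The regression also has limits. Where the groups' concentrations hardly overlap it extrapolates, and it does not remove the effect of top-ups on later pain scores and satisfaction. That argues against making it the sole reported result. It does not answer the absence of any adjustment or caution in the plan.

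**Conclusion.** The point holds for the secondary analyses. For requests before 8 cm the result is arithmetic: the rate is tied to 50% plus k/(2n), and no plausible gap in concentration makes an unadjusted comparison significant unless a group reaches the 0% floor. For pain and satisfaction the conclusion is conditional. The planned tests have almost no power for a mode difference that acts through analgesic adequacy (about 2–5% rejection under the assumed models), but may detect a direct mode effect at equi-effective concentrations. Motor weakness and hypotension comparisons carry the concentration difference along with mode; motor weakness was simulated, and hypotension rests on the same reasoning without a calculation. The EC50s, SDs and outcome models are assumptions, since the documents give none. The request result does not depend on them away from the floor and is the same under both readings of the sample size. The primary MLAC comparison is unaffected and remains the efficacy contrast.

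**What to change.** In the clinical-outcome analysis under iv. Additional Data Points:

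- Keep the planned two-sample tests, labelled as comparisons at approximately equi-effective concentrations.
- Alongside them, report a regression of pain, satisfaction, motor weakness and hypotension on group plus assigned bupivacaine concentration (linear or logistic as the outcome requires). Assigned concentration is a valid covariate because it is set by earlier women's outcomes, before her own is known.
- Show the distribution of concentrations by group and the share of women in the common range.
- State that a null on pain, requests or satisfaction is not evidence that the modes are equally effective, and that efficacy is judged on the MLAC.

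The cost is SAP wording and a few extra models; the assigned concentration is already known for every woman, because the rule cannot run without it. The drawback is that, where overlap is small, the adjusted contrast leans on the model form and its interval widens. It should therefore be specified as supportive.

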**Specific aims and basic hypothesis**

There is limited data on the mechanism of action for short acting opioids in the presence of local anesthetic in the epidural space. The recent popularization of administering epidural local anesthetic with opioid by programmed intermittent boluses (PIEB) for labor analgesia may be preferential to the traditional continuous epidural (CEI) infusion of solution for maintenance analgesia.

The aims of the study are to first determine the relative potency of PIEB compared to CEI and secondly to determine the mechanism to explain the potential PIEB efficacy advantage. The study aims will be accomplished by utilizing a validated minimal local analgesic concentration (MLAC) study design.

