### **Significance**

These findings will facilitate a better understanding of the mechanism of action of short acting opioids in the presence of local anesthetic in the epidural space, which have the potential of optimizing strategies to provide maintenance of labor analgesia. Part 1 of our study will determine relative potency of PIEB compared for labor analgesia to CEI using MLAC to better facilitate appropriate initial epidural pump settings and maternal dosing. Part 2 of our study will determine mechanism to explain the PIEB efficacy advantage, so that the epidural technique can be optimize.

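### No between-group MLAC comparison is specified, and whether each part continues past 10 per group depends on an undefined difference

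*Combined protocol and SAP*

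**What the plan says.** All of this is in the combined protocol and SAP.

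- **Aim.** Specific aims: "The aims of the study are to first determine the relative potency of PIEB compared to CEI". Significance repeats it: "Part 1 of our study will determine relative potency of PIEB compared for labor analgesia to CEI using MLAC". The second aim, mechanism, rests on Part B and also needs a comparison of two groups.
- **Primary outcome** (section iv, Additional Data Points): "the minimal local anesthetic concentration of the final participants in each respective group upon study completion".
- **MLAC analysis** (same section): "The median effective concentrations will be estimated from the up-down sequences using the method of Dixon and Massey". The only inferential output named is one estimate per group, from a method "that will enable MLAC with 95% confidence interval (CI) to be derived". Probit regression of the sequences is the back-up.
- **Two-sample tests** (same section): "Demographic, obstetric and clinical outcome measures data will be analyzed using" the t, Mann-Whitney and chi-squared or Fisher tests. MLAC is treated in its own paragraph.
- **Interim timing** (same section): "Interim analysis will be performed at 20 patients (10 in each group) in study part A and B, respectively".
- **Interim consequence** (same section). The final size is tied to the result of that look: when "no important differences are detected, the study will end with the recruitment of 160 patients", a total that the plan also gives as 80 per study group. The plan does not say what counts as important, which statistic is used, or what happens if a difference is found.

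**The concern.** Relative potency is a between-group quantity, and the plan stops one step short of it. The data can supply a contrast, so this is a gap in pre-specification and the aim remains reachable. The open choice still matters. A normal-theory test of the ratio and a comparison of the two planned intervals can give different answers on the same data, and nothing fixes which will be used before the results are known.

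The interim rule is the more serious half. Reaching full size is conditional on a judgement at 10 per group, where Dixon-Massey standard errors are least reliable. If a part can end there, false-positive error is uncontrolled, and a textbook boundary would not restore control.

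A smaller wording point: taken literally, an MLAC of the final participants is a single concentration on the 0.01% grid, whose precision does not improve with sample size. The MLAC paragraph uses the whole sequence. The two should agree.

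**Working it through.** **Inputs from the protocol.** Start 0.06%, step 0.01%, down after success and up after failure (Experimental design); interim at 10 per group. Final size is ambiguous: 160/2 = 80 per group, but the design has four groups and 160/4 = 40. Both are shown. The stated size cannot be reproduced, because alpha, power, difference and SD are not given.

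**Assumptions (not in the documents).** Normal tolerance with SD 0.01-0.03%; equal true MLACs of 0.05-0.07%; two-sided testing; stopping on the MLAC contrast.

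**Estimator.** The mean concentration at the less frequent response, shifted half a step. Its standard error is SE = 1.62 × step × (M + 0.029)/√N, where N is the number of those responses and M their variance in squared steps. The test is z = |ln(MLAC1/MLAC2)| / √[(SE1/MLAC1)² + (SE2/MLAC2)²].

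**Why n = 10 is a problem.** If a sequence of 10 alternates between two adjacent concentrations, N = 5 and M = 0. Then SE = 1.62 × 0.01 × 0.029/√5 = 0.0002%. With the small-variance floor, which holds the estimated SD at 0.53 step or more, SE = 0.53 × 0.01/√5 = 0.0024%, about 11 times larger. Interim results are therefore given both ways.

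**What normal theory would promise.** With independent increments, 0.05 at both looks gives 9.1% (10 of 40) or 9.4% (10 of 80). Using 0.001 then 0.05 gives 5.1% either way.

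**What the up-down rule gives** (40,000 simulated trials per setting, 25 settings; ranges across settings; a separate simulation on a coarser set of settings agreed closely):

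| Two-sided error, no true difference | 40 per group | 80 per group |
|---|---|---|
| Final look only, 1.96 | 7.6-10.1% | 5.8-6.8% |
| Final look only, non-overlap of the two 95% CIs | 2.2-3.8% | 1.1-1.6% |
| 0.05 at both looks, no floor | 25.9-35.3% | 25.5-33.7% |
| 0.05 at both looks, with floor | 18.9-33.1% | 18.3-31.3% |
| 0.001 then 0.05, no floor | 13.0-20.9% | 12.0-18.3% |
| 0.001 then 0.05, with floor | 9.6-18.9% | 8.4-16.3% |

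The floor does not materially change the final-look rows. The excess comes from the interim: at 10 per group without the floor, z exceeds 1.96 in 20.8-29.5% of trials and 3.29 in 6.0-13.0% (about 2-11% with the floor).

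**Same data, different answers.** With true MLACs of 0.05% and 0.06%, the ratio test is significant while the two CIs overlap in 12-19% of trials at 40 per group and 4-26% at 80.

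**Critical value for 5% error at the final look.** The simulated values are 2.21-2.45 at 40 per group and 2.03-2.12 at 80. Relative to 1.96, the log-scale CI widens by 2.21/1.96 = 1.13 to 2.45/1.96 = 1.25 at 40, and by 2.03/1.96 = 1.04 to 2.12/1.96 = 1.08 at 80.

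**What an interim stop could gain.** A true 0.1% interim boundary is large and poorly determined: simulated values run from about 5 to above 15, depending on the SE version and the setting. With one no-floor boundary of about 15.5 that covers every assumed SD, power to detect 0.04% against 0.06% is 1.4%, 0.5% and 0.4% at SD 0.01, 0.02 and 0.03%.

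**The case against.** **The comparison is plainly intended and can be derived.** True, and it limits the point to pre-specification. It would be wrong to infer that the trial cannot answer its aim. The named two-sample tests do not close the gap: they are assigned to other data, and they would ignore that each concentration depends on the previous patient's response. The probit back-up has no stated group term.

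**Early stopping is inferred.** This stands. The text says what happens when no important difference is seen and is silent on the alternative. A reader might conclude that this trial has a false-positive rate of about a third. The documents do not support that. The figure needs stopping on the MLAC contrast, a normal-theory test and a nominal 0.05 threshold, none of which the plan states. Non-overlap of intervals is likewise never named as a test.

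**The interim figures depend on the SE version.** This also stands, hence both sets. With the floor they are lower, but still well above 5%.

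**The 1.4% interim power is not a general ceiling.** Correct. With the boundary matched to a known SD of 0.01%, power is about 5.5% without the floor and about 19% with it. The near-zero figure applies when one boundary must cover an unknown SD.

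**At 80 per group the final-look distortion is small.** Agreed: 6-7% against 5%. Calibration of the final test matters mainly if groups are 40, and it is one reasonable method among several.

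**The primary outcome wording may be loose drafting.** Probably so, since the MLAC paragraph in the same section uses the sequences. It should not be read as proof that only the last concentrations will be analysed.

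**Conclusion.** The point holds as a pre-specification gap that should be fixed. The plan promises relative potency, defines no between-group contrast, and makes continuation depend on an undefined difference at 10 per group.

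The error rates illustrate what common choices would do under the assumed tolerance SDs; they are not properties of the plan. Their firm message is that conventional normal boundaries do not control error at 10 per group: even 0.001 then 0.05 gives about 12-21%, or 8-19% with the floor, where normal theory promises 5.1%. At the final look the choice of method alone moves error from 2-4% to 8-10% at 40 per group, and from 1-2% to 6-7% at 80.

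**What to change.** 1. **Interim.** State that the look at 10 per group does not permit stopping for a difference. If stopping is kept, name the contrast and set the boundary by simulating the up-down rule so that overall two-sided error is 0.05; do not borrow a normal boundary.
2. **Primary comparison.** Replace the primary outcome sentence and extend the MLAC paragraph, for example: *The primary outcome is the bupivacaine MLAC estimated from the full up-down sequence in each group. The primary comparison in each part is the ratio of MLACs (Part A: Group 2 / Group 1; Part B: Group 4 / Group 3), with a 95% CI from the standard error of the log ratio. Probit analyses remain as back-up.*
3. **Optional, mainly if groups are 40.** Replace 1.96 with a critical value calibrated by simulation at the planned group size over a stated range of tolerance SD.

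**Cost.** Wording for items 1 and 2, a small simulation if a boundary or critical value is calibrated, and no new data or recruitment. Barring the interim stop gives up very little when the SD is unknown. Calibration widens the CI by about 13-25% at 40 per group or 4-8% at 80, with some loss of power. It is not complete protection: if the tolerance SDs differ threefold (0.01% against 0.03%), error is still about 6%, even at slightly conservative critical values of 2.5 (40 per group) and 2.15 (80 per group).
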